2.2.2. Clinical development

Phase 1 study

The futuximab/modotuximab Sym004-01 was a Phase 1 dose escalation study that included a total of 111 patients (20 patients with refractory or recurrent advanced solid tumours in the Phase 1a dose escalation part and 91 patients with heavily pre-treated mCRC and acquired resistance to previous anti-EGFR therapy into five Phase 2 dose expansion cohorts). The recommended Phase 2 dose (R2PD) levels of two regimens of futuximab/modotuximab were defined based on safety and tolerability and were identified as 12 mg/kg when administered weekly and 18 mg/kg when administered on a every two weeks schedule. The adverse effect profile was similar to that observed with previously studied anti-EGFR mAbs with no novel safety findings identified, although cutaneous toxicity and hypomagnesemia were observed more frequently and were more severe in patients treated with futuximab/modotuximab at the R2PD on each of these schedules. This apparent difference in the AE profile may be due to differences in the doses or schedule of futuximab/modotuximab utilised, differences due to its unique MoA, or to the potential enrichment for patients likely to manifest these specific AEs. As it has been documented in other studies, cutaneous AEs and hypomagnesemia have been shown to be associated with responsiveness to anti-EGFR therapies,^{19,20} and the patients studied in cohorts B-F were selected based on documented development of refractoriness following prior response to or prolonged disease stabilisation (> 16 weeks) while receiving one or more of the available anti-EGFR mAbs (cetuximab, panitumumab) approved for the treatment of mCRC.

Two dosage regimens cohorts (Parts B: 12 mg/kg weekly and F: 9 mg/kg loading dose followed by 6 mg/kg weekly) were chosen for further evaluation in subsequent trials. Confirmed objective response rate was 6.9% (2/29 patients) and 0% (0/20 patients) with 12 mg/kg and 9/6 mg/kg dose regimens, respectively.

Phase 2 study

The futuximab/modotuximab Sym004-05 is an open-label, randomised, controlled, multicentre, Phase 2 trial that enrolled 254 patients with mCRC cancer refractory or intolerant to chemotherapy (5-FU, irinotecan and oxaliplatin), who had responded to and progressed on prior anti-EGFR mAb therapy (*i.e.* acquired resistance to anti-EGFR mAbs).

[figure not shown]

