8.11. Management of treatment dose adaptations due to toxicities

For participants who have experienced a dosing modification, reasons for dose modifications or delays, the supportive measures taken, and the outcome will be documented in the participant's source documents and recorded in the e-CRF.

In the futuximab/modotuximab plus trifluridine/tipiracil arm doses of either futuximab/modotuximab, or trifluridine/tipiracil, or both drugs can be modified, depending on the toxicity observed.

General rules:

Before starting a new treatment cycle, toxicity must have resolved as specified in the [Sections 8.11.1](#) and [8.11.2](#) and the safety criteria to be met as specified in the [Section 6.1.5](#).

- If toxicity due to any of the IMPs does not resolve during the given cycle to Grade 1 or baseline, the start of the next cycle will be delayed for a maximum of 30 days for trifluridine/tipiracil and 21 days for futuximab/modotuximab (see [Sections 8.11.1](#) and [8.11.2](#)). If more than the maximum delay period is needed for recovery, the next cycle should be started with the IMP not concerned by the toxicity.
- If, in the opinion of the investigator, the toxicity is clearly related to one of the treatments, reduction of one and not the other agent is appropriate. If, in the opinion of the investigator, the toxicity is related to the futuximab/modotuximab only futuximab/modotuximab should be reduced according to recommended dose modifications. If, in the opinion of the investigator, the toxicity is related to the trifluridine/tipiracil only trifluridine/tipiracil should

be reduced according to recommended dose modifications. If the toxicity is related to the combination of two agents, both agents should be reduced (if applicable), interrupted or discontinued according to the recommended dose modifications.

- Participants may have trifluridine/tipiracil discontinued and continue on futuximab/modotuximab alone. Similarly, participants may discontinue futuximab/modotuximab and continue on trifluridine/tipiracil alone if appropriate.

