8.11.2.2. Dose Delay

Toxicities may be managed by delay in dosing, provided they do not meet the criteria for IMP discontinuation ([Section 5.8.1](#)). In such cases, the period between any 2 scheduled doses may be extended up to 3 days (inclusive) to allow an improvement of the toxicity. Such delays will be considered an extension within the current cycle. If a delay of more than 3 days from the scheduled dose date is necessary, the dose should be omitted and proceed to the next scheduled dose (i.e. 14 days from the last dose).

If 3 consecutive doses are needed to be omitted (i.e. more than 21 days from the last dose of futuximab/modotuximab), the participant should be discontinued from futuximab/modotuximab. All delays of futuximab/modotuximab must be documented on the appropriate page of the participant's e-CRF.

If toxicity does not resolve during the given cycle to Grade 1 or baseline, the start of the next cycle may be delayed by a maximum of 21 days from the last dose of futuximab/modotuximab administered to allow the initiation of both IMPs at the same time in the next cycle. If more than 21 days from the last dose administered are needed for recovery, futuximab/modotuximab should be discontinued and the next cycle will start with only trifluridine/tipiracil.

Dosing may be restarted at the same dose, as clinically indicated. However, administration of futuximab/modotuximab may only be restarted provided retreatment criteria are met ([Section 6.1.5](#)).

For treatment restart with no dose reduction:

- If treatment restart after the omission of 1 dose (i.e. treatment delay up to 14 days from the last dose), it is recommended that dosing restart with maintenance dose of 6 mg/kg;
- If treatment restart after the omission of 2 consecutive doses (i.e. treatment delay up to 21 days from the last dose), it is recommended that dosing re-start with the re-administration of a loading dose of 9 mg/kg followed by weekly maintenance doses of 6 mg/kg.

For treatment restart with dose reduction, see Section 8.11.2.3.

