10.1.2.4.2. Randomised Part

Primary objective

The primary objective is to demonstrate the superiority of futuximab/modotuximab in combination with trifluridine/tipiracil over trifluridine/tipiracil monotherapy in terms of OS in participants with chemotherapy pre-treated (including oxaliplatin, irinotecan and 5-fluorouracil, anti-VEGF agents, and anti-EGFR mAb therapy for ≥ 16 weeks) metastatic colorectal cancer that are KRAS/NRAS and BRAF WT (Double negative [DN]).

Key secondary objective

The key secondary objective is to demonstrate the superiority of futuximab/modotuximab in combination with trifluridine/tipiracil over trifluridine/tipiracil monotherapy in terms of OS in participants with chemotherapy pre-treated (including oxaliplatin, irinotecan and 5-fluorouracil, anti-VEGF agents, and anti-EGFR mAb therapy for ≥ 16 weeks) metastatic colorectal cancer that are KRAS/NRAS, BRAF WT and EGFR-extracellular domain WT (Triple negative [TN]).

Secondary objectives

Secondary objectives are to estimate the effect of futuximab/modotuximab in combination with trifluridine/tipiracil *versus* trifluridine/tipiracil monotherapy in terms of PFS, OR, DC, DoR, TTNT, TTR, and TtPS2 in participants with chemotherapy pre-treated (including oxaliplatin, irinotecan and 5-fluorouracil, anti-VEGF agents, and anti-EGFR mAb therapy for ≥ 16 weeks) metastatic colorectal cancer.

Other secondary objectives are to compare the safety and tolerance, and the impact on QoL of futuximab/modotuximab in combination with trifluridine/tipiracil to trifluridine/tipiracil monotherapy in participants with chemotherapy pre-treated metastatic colorectal cancer.

Intercurrent events

During the study the following intercurrent events could occur:

- Administration of further anti-cancer therapy.
- Treatment discontinuation.
- Treatment switch (from futuximab/modotuximab in combination with trifluridine/tipiracil to trifluridine/tipiracil monotherapy and from trifluridine/tipiracil monotherapy to futuximab/modotuximab in combination with trifluridine/tipiracil).

Estimands of interest

The attribute treatment will be the same for all estimands of interest:

- Treatment: Futuximab/modotuximab + trifluridine/tipiracil *versus* trifluridine/tipiracil monotherapy.

The following estimands will be studied:

Table (10.1.2.4.2) 1 - Studied estimands

Estimand	Variable	Population level summary	Handling intercurrent events (IEs)	Population

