- For IE “administration of further anti-cancer therapy” and “treatment switch”: data obtained post IE will not be used for the analysis. OS will be censored at the time of administration of further anti-cancer therapy.
- For IE “treatment discontinuation”: time of death for any cause after treatment discontinuation will be taken into account.

These strategies are aligned with those estimands.

The distribution of OS will be compared between the two treatment groups using a stratified log-rank test at one-sided 2.5% level of significance (stratification factors based on IWRS data).

For missing data (not linked to intercurrent events), *i.e.* participants without documentation of death (lost to follow-up, withdrawal of consent, administrative end of study), the OS will be censored on the last contact date the participant was known to be alive or the cut-off date, whichever is earlier.

Other estimands will be defined in the SAP if necessary.

10.1.2.4.2.4. Secondary estimands based on PFS, OR, DC, DoR, TTNT, TTR and TtPS2

Secondary estimand based on PFS

One secondary estimand of interest is the effect of the randomised treatments on progression-free survival in all subjects before participants receive further anti-cancer therapy (while on treatment strategy). For participants who start the subsequent anti-cancer therapy before disease progression or death will be censored at the date of last evaluable tumour assessment prior to the date of any subsequent anti-cancer therapy. This is aligned with the estimand and the while on treatment strategy.

The other secondary estimand of interest is the effect of the randomised treatments on progression-free survival in all subjects regardless of whether or not intercurrent events occur (treatment policy strategy). All data collected during the trial regardless of occurrence of an IE will be used. This is aligned with the treatment policy strategy.

The following analyses will be done as primary analyses:

- The distribution of PFS will be compared between the two treatment groups using a stratified log-rank test at one-sided 2.5% level of significance (stratification factors based on IWRS data).
- PFS for each arm will be summarized using Kaplan Meier curves and further characterised in terms of the median and survival probabilities at 2, 4, 6 and 8 months along with the corresponding 2-sided 95% CI for the estimates.

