- The hazard ratio of PFS with its 95% confidence interval will be estimated with a stratified Cox proportional hazard model (stratification factors based on IWRS data).

The following analyses will be done as sensitivity analyses:

- An analysis that considers clinical progression and administration of further anti-cancer therapy as PFS events in addition to the radiological progression or death.
- PFS analysis based on PPS.

For missing data (not linked to intercurrent events), *i.e.* participants who were lost to follow-up or who have withdrawn their consent without radiological progression or reached the time point of analysis without a known record of death or radiological progression, the PFS will be censored at the date of last evaluable tumour assessment or the cut-off date, whichever is earlier.

The same subgroup analyses as used for the primary estimand will be done for PFS.

Secondary estimands based on ORR and DCR

Other secondary estimand of interest are the effect of the randomised treatments on response in all subjects before participants receive further anti-cancer therapy.

Responses recorded after intercurrent event will be excluded. This is aligned with the estimand and the treatment while on treatment strategy.

The following analyses will be done:

- OR based on the investigator's tumour assessment will be compared in the FAS between treatment arms using a stratified Cochran-Mantel-Haenszel (CMH) test. A 2-sided 95% CI for the difference in ORR between the two treatment arms will also be provided based on the normal approximation. If required, a Fisher's exact test and 2-sided 95% Clopper-

Pearson CIs will be used. A 2-sided 95% CI for the difference in ORR between the two treatment arms will also be provided based on the normal approximation.

- DC based on the investigator's tumour assessment will be compared in the FAS between treatment arms using a stratified CMH test. A 2-sided 95% CI for the difference in DCR between the two treatment arms will also be provided based on the normal approximation. If required, a Fisher's exact test and 2-sided 95% Clopper-Pearson CIs will be used. A 2-sided 95% CI for the difference in DCR between the two treatment arms will also be provided based on the normal approximation.

Secondary estimands based on DoR, TTNT, TTR and TtPS2

Responses recorded after intercurrent event will be excluded. This is aligned with the estimand and the treatment while on treatment strategy.

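### A permitted antibody stop in Arm A is classed as a treatment switch, so the supplementary OS rule discards later data that its own estimand would keep

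*Protocol*

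**What the plan says.** Protocol section 10.1.2.4.2 lists three intercurrent events: further anti-cancer therapy, treatment discontinuation and treatment switch. The last is defined in both directions: "Treatment switch (from futuximab/modotuximab in combination with trifluridine/tipiracil to trifluridine/tipiracil monotherapy", and "from trifluridine/tipiracil monotherapy to futuximab/modotuximab in combination with trifluridine/tipiracil".

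The toxicity rules describe the first direction as routine management. Section 8.11 says that "participants may discontinue futuximab/modotuximab and continue on trifluridine/tipiracil alone if appropriate". Section 8.11.2.2 directs it when recovery takes more than 21 days from the last antibody dose: "futuximab/modotuximab should be discontinued and the next cycle will start with only trifluridine/tipiracil". Section 8.11 also allows the mirror-image step: "Participants may have trifluridine/tipiracil discontinued and continue on futuximab/modotuximab alone". That step is not listed as a switch.

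For the supplementary OS estimands (double-negative and triple-negative populations), section 10.1.2.4.2.3 groups further therapy and treatment switch and states: "data obtained post IE will not be used for the analysis. OS will be censored at the time of administration of further anti-cancer therapy". The next bullet says that deaths after treatment discontinuation are taken into account. Table (10.1.2.4.2) 1 and the opening of 10.1.2.4.2.3 limit the estimand to the time before further anti-cancer therapy. The stated aim is to remove the effect of another therapy.

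For OR and DC, section 10.1.2.4.2.4 says: "Responses recorded after intercurrent event will be excluded". The sentence is repeated for DoR, TTNT, TTR and TtPS2. The while-on-treatment PFS rule in the same section censors only at subsequent anti-cancer therapy.

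**The concern.** An Arm A participant who stops the antibody for toxicity and stays on trifluridine/tipiracil is still on part of the assigned regimen and has received no other therapy. The estimand as defined would keep following that person. The data rule appears to stop. An Arm A participant who stops both drugs, or an Arm B participant who stops the only drug, is a discontinuation and the death counts.

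Two things are at stake. First, the rule cannot be programmed as written, because the same stop can be read as a switch or as a discontinuation, and a switch without further therapy has no date attached. Second, if the switch reading is applied, follow-up is cut in one arm for a reason tied to toxicity. Section 2.2.2 notes that "cutaneous AEs and hypomagnesemia have been shown to be associated with responsiveness to anti-EGFR therapies", so it is plausible, though not shown, that those who switch differ in prognosis from those who do not.

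**Working it through.** **The plan's own figure.** The only relevant design figure is the 90% power for primary OS in section 10.2 (383 events, HR 0.71 or 8.5 vs 12 months, one-sided 0.025). Fixed-design check: events needed = 4(1.960 + 1.282)² / (ln 0.71)² = 359; power at 383 events = 0.918. With the stated interim efficacy and futility bounds, simulated power is 0.897 (HR 0.71) to 0.900 (HR 8.5/12). The figure reproduces. It is untouched here, because primary OS uses all data regardless of intercurrent events.

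**The rules side by side (supplementary OS)**

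| Event | Arm | Handling as written |
|---|---|---|
| Stops all study treatment | A or B | Discontinuation: deaths count |
| Stops antibody, keeps trifluridine/tipiracil | A only | Listed as a switch: later data not used, no date given. Sections 8.11 and 8.11.2.2 call it discontinuing the antibody: deaths would count |
| Stops trifluridine/tipiracil, keeps antibody | A only | Not listed as a switch |
| Starts the antibody | B | Listed as a switch. No crossover route described; section 6.5 says the product is not on the market |
| Further anti-cancer therapy | A or B | Censored at its start |

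The second row has three readings: censor at the switch, censor only at further therapy (the only date given), or treat as discontinuation. Only the first removes data, and the sizes below apply to it.

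**Deaths removed.** Assumed switch rates: 6% (the phase 2 rate of adverse events leading to discontinuation on the 9/6 regimen, section 2.2.4, given there as antibody alone) and 15% (assumed). Arm A has 500/2 = 250 participants. Simulating exponential OS at the design effect up to 383 deaths gives about 178 Arm A deaths, or 178/250 = 0.71 per participant.
- 6%: 250 × 0.06 = 15 switchers; 15 × 0.71 ≈ 11 deaths removed.
- 15%: 250 × 0.15 = 37.5 switchers; 37.5 × 0.71 ≈ 27 deaths removed.
- Arm B: 0 through this event.

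These counts are on the high side, because some participants would die before switching.

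**Effect on the hazard ratio.** Simulation with 200,000 per arm, true HR 1.00, control median 8.5 months, gamma frailty with variance 0.5, switch times uniform over 0.7 to 3 months and drawn independently of the death time given frailty, and Arm A switchers censored at the switch:

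| Switch rate | Unrelated to prognosis | From better-prognosis half | From worse-prognosis half |
|---|---|---|---|
| 6% | 1.00 | 1.03 | 0.97 |
| 15% | 1.00 | 1.07 to 1.08 | 0.93 |

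For scale, the standard error of the log hazard ratio with 383 events is about 2/√383 = 0.10. Since ln 1.03 = 0.03 and ln 1.08 = 0.08, the shifts are about 0.3 and 0.8 of a standard error.

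**Response endpoints.** Section 10.1.2.4.2.4 excludes responses after an intercurrent event and exempts none of the three. Table (10.1.2.4.2) 1 stops OR and DC only at further anti-cancer therapy. The data rule is therefore broader than the estimand in both arms, and it differs from the while-on-treatment PFS rule.

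**The case against.** The strongest reply is that the plan is ambiguous rather than wrong. Sections 8.11 and 8.11.2.2 speak of discontinuing the antibody, so the stop can be read as treatment discontinuation, where deaths count; and the only censoring date given is that of further therapy. This stands as a description. It does not rescue the text, because the intercurrent-event list names the same step as a switch and the two categories are handled in opposite ways.

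Three stronger readings are tempting and are not supported.
- A reader might infer that responses are lost in Arm A only. The exclusion also covers treatment discontinuation and further therapy, which occur in both arms.
- A reader might infer that the supplementary hazard ratio is biased whatever happens, even under the null. With switching unrelated to prognosis it stays at 1.00. The sentence in section 2.2.2 links adverse events to anti-EGFR response. It says nothing about who stops the antibody, and it does not fix the sign of any bias.
- A reader might infer that the trial's main result is at risk. Primary and key secondary OS follow a treatment-policy strategy and keep all data, and a treatment-policy PFS estimand is also planned.

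The switch rates are also weakly grounded. In the phase 2 trial discontinuation meant stopping the only study drug, and the documents give no rate for the combination.

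**Conclusion.** The inconsistency is in the text and holds. A permitted, in one case directed, antibody stop is classed as a switch; its later OS data are discarded without a censoring date; and this conflicts with an estimand and an aim that concern only further or other therapy. Because only Arm A can stop the antibody and Arm B has no described route to it, this event in practice removes OS follow-up in one arm. The response rule is broader than its estimand in both arms.

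The size is modest and conditional. If switching is related to prognosis, the supplementary hazard ratio moves by about 3% at 6% switching and by 7 to 8% at 15%, in an unknown direction. If it is unrelated, about 11 or 27 Arm A deaths are lost without bias. Rates, timing and frailty are assumptions. SAP version 2.0 records that the randomised part was cancelled and omits these analyses, so the point concerns the protocol as written.

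**What to change.** Analysis wording only; no dosing or stopping rule changes.

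1. In the intercurrent-event list of 10.1.2.4.2, restrict *treatment switch* to receipt of the other arm's investigational drug, which is not part of the participant's assigned regimen.
2. Classify stopping either investigational product, with or without the other, as treatment discontinuation within the assigned regimen. Count deaths and responses until further anti-cancer therapy.
3. In 10.1.2.4.2.3, state the censoring date for a true switch.
4. In 10.1.2.4.2.4, limit the exclusion to responses after further anti-cancer therapy, matching Table (10.1.2.4.2) 1 and the while-on-treatment PFS rule.

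The cost is a few sentences of protocol text and the matching derivation rules. No new data are needed: the protocol already has stops of each product, their reasons and subsequent anticancer therapy recorded. As the randomised part was cancelled, the change matters only if this design or its text is reused.

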Primary estimand: effect of the randomised treatments on the survival duration in all subjects that are KRAS/NRAS and BRAF WT (Double negative [DN]) regardless of whether or not intercurrent events occur	OS	HR	Treatment policy strategy	FAS
Key secondary estimand: effect of the randomised treatments on the survival duration in all subjects that are KRAS/NRAS, BRAF WT and EGFR-extracellular domain WT (Triple negative [TN]) regardless of whether or not intercurrent events occur	OS	HR	Treatment policy strategy	FAS restricted to Triple negative [TN] subjects
Effect of the randomised treatments on the survival duration in all subjects that are KRAS/NRAS and BRAF WT (Double negative [DN]) before participants receive further anti-cancer therapy	OS	HR	While on treatment strategy	FAS
Effect of the randomised treatments on the survival duration in all subjects that are KRAS/NRAS, BRAF WT and EGFR-extracellular domain WT (Triple negative [TN]) before participants receive further anti-cancer therapy	OS	HR	While on treatment strategy	FAS restricted to Triple negative [TN] subjects
Effect of the randomised treatments on progression-free survival before participants receive further anti-cancer therapy	PFS	HR	While on treatment strategy	FAS
Effect of the randomised treatments on progression-free survival regardless of whether or not intercurrent events occur	PFS	HR	Treatment policy strategy	FAS
Effect of the randomised treatments on response before participants receive further anti-cancer therapy	OR DC	Risk difference	While on treatment strategy	FAS

Table (10.1.2.4.2) 1 (Cont'd) - Studied estimands

Estimand	Variable	Population level summary	Handling intercurrent events (IEs)	Population
Effect of the randomised treatments on the response duration before participants receive further anti-cancer therapy	DoR	HR	While on treatment strategy	FAS
Effect of the randomised treatments on the time from the randomisation to initiation of the next systemic anti-cancer therapy	TTNT	HR	While on treatment strategy	FAS
Effect of the randomised treatments on the time from randomisation until first radiologically confirmed tumour response (CR or PR) before participants receive further anti-cancer therapy	TTR	HR	While on treatment strategy	FAS
Effect of the randomised treatments on the time from the date of randomisation to the date when ECOG PS score of ≥ 2 is observed for the first time before participants receive further anti-cancer therapy	TtPS2	HR	While on treatment strategy	FAS

With:

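### The ORR/DCR exclusion rule does not name its intercurrent event; read literally, it contradicts the estimand it claims to match

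*Protocol*

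**What the plan says.** - **Intercurrent events.** Protocol 10.1.2.4.2 opens its list with "During the study the following intercurrent events could occur" and names three: further anti-cancer therapy, "Treatment discontinuation", and a switch, given as "Treatment switch (from futuximab/modotuximab in combination with trifluridine/tipiracil to trifluridine/tipiracil monotherapy" and also in the reverse direction.
- **Estimand.** The OR/DC row of Table (10.1.2.4.2) 1 reads "Effect of the randomised treatments on response before participants receive further anti-cancer therapy". The summary is a risk difference in the FAS, and the strategy column says while on treatment. Section 10.1.2.4.2.4 repeats the definition: "the effect of the randomised treatments on response in all subjects before participants receive further anti-cancer therapy".
- **Rule.** The next line is "Responses recorded after intercurrent event will be excluded. This is aligned with the estimand and the treatment while on treatment strategy". The same two sentences appear again for DoR, TTNT, TTR and TtPS2.
- **Same label elsewhere.** Supplementary OS (10.1.2.4.2.3) goes event by event. Data after further therapy or a switch are not used, but for discontinuation "time of death for any cause after treatment discontinuation will be taken into account". The while-on-treatment PFS analysis censors for subsequent anti-cancer therapy only.
- **BOR window.** Protocol 7.2.5 ends it when treatment ends. Table (3.4) 1, for the Safety Lead-In, runs it to progression or recurrence.
- **Scans.** Under 5.8.2 and 7.2.1, participants who stop without radiologic progression are scanned every 8 weeks until it occurs.
- **SAP V2.0.** The randomised part is removed and BOR in the lead-in is the only response analysis left. SAP 6.1 leaves out follow-up e-CRF data and, where applicable, responses after intercurrent events. The SAP contains no list of those events.

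**The concern.** Take a participant who stops study treatment without progression and has a scan before any new therapy. By the estimand's wording that scan counts. By the rule's literal wording it does not, yet the rule says the two agree.

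Two routes could change a result. For DC, the stop may come before the first scheduled scan at 8 weeks, so that stable disease or response is seen only afterwards. For OR, which must be confirmed in the randomised part, the confirming scan may fall after the stop. An Arm A participant who stops only the antibody raises a further question, because a switch is also a listed event.

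Two programmers working from this text could produce different ORR and DCR. The RECIST text in Appendix 7 asks protocols to be clear on whether post-treatment assessments count and to specify how new therapy affects best response.

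**Working it through.** **1. The texts side by side.** The first three rows are all labelled while on treatment.

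| Source | After further therapy | After discontinuation | After switch |
|---|---|---|---|
| Supplementary OS | not used | used | not used |
| PFS | censored | no cut | not mentioned |
| OR/DC, definition | outside | inside | not mentioned |
| OR/DC, rule read literally | excluded | excluded | excluded |
| OR/DC, rule read as further therapy only | excluded | kept | kept |

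The literal reading disagrees with the definition in the discontinuation column. The narrow reading agrees, but leaves switch to be settled by inference.

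**2. The plan's own figure.** None is given for ORR or DCR. The power stated for the final comparison is for OS: 90% with 383 events, HR 0.71, one-sided 0.025. Simulating the Table (10.2) 1 bounds at 128, 255 and 383 events (3 million draws) gives 89.6% at HR 0.71 and 90.0% at 8.5/12 = 0.708. The figure reproduces, and the response rule does not touch it.

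**3. Illustration for ORR.** Responders lost = n × rate × d × q. Here d is the share stopping without progression before the qualifying scan, and q is the share of those whose response is recorded only after the stop.

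Inputs:
- n = 250 per arm (500 randomised 1:1, section 10.2).
- d = 6%, or 14.5%: the Phase 2 TEAE discontinuation rates for the 9/6 and 12 mg/kg arms (2.2.2), borrowed as an assumption.
- Rate 9.6% (Phase 2, 9/6 arm), or 37.0% (the panitumumab combination study in 2.3.2, in anti-EGFR-naive patients, used only as an upper end).
- q = 0.5 to 1, assumed.

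Results for Arm A:
- Rate 9.6%, d = 6%: 250 × 0.096 × 0.06 × (0.5 to 1) = 0.72 to 1.44 responders, or 0.3 to 0.6 points.
- Rate 37.0%, d = 6%: 250 × 0.37 × 0.06 × (0.5 to 1) = 2.78 to 5.55 responders, or 1.1 to 2.2 points.
- Rate 9.6%, d = 14.5%, q = 1: 3.48 responders, or 1.4 points.

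For scale, with 2.9% in Arm B (Phase 2 control), the SE of the ORR difference is √[(0.096 × 0.904 + 0.029 × 0.971)/250] = 2.1 points. It is 3.2 points with 37.0% in Arm A.

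**4. Illustration for the DCR difference.** Assume an equal true rate r in both arms, from 30% (assumed) to 81.4% (same panitumumab study), and q = 1. Shift = r × (d in Arm A − d in Arm B).
- 6% v 0%: 0.30 × 0.06 = 1.8 to 0.814 × 0.06 = 4.9 points against Arm A.
- 6% v 3%: 0.9 to 2.4 points against Arm A.
- 3% v 6%: 0.9 to 2.4 points in favour of Arm A.

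The SE, √[2r(1 − r)/250], is 4.1 points at r = 0.30 and 3.5 at r = 0.814.

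**5. The lead-in.** SAP Table (5.1.2) 1 admits tumour assessments up to 30 days after last intake, and the withdrawal visit falls within 4 weeks. A withdrawal scan is thus inside the window, but excluded if discontinuation counts as an intercurrent event. With about 25 participants planned, one reclassification moves a BOR category by 1/25 = 4 points.

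**The case against.** - **The rule may mean further therapy only.** It does not say any or all events, the sentence before it names further anti-cancer therapy, and it claims alignment with that estimand. This is a fair reading, and it is why the point is an ambiguity and not a proven rule to drop every off-treatment response. The reader still has to choose. Section 10.1.2.4.2 promises that the handling of intercurrent events will be detailed, and for response it is not.
- **The exclusion may be the estimand.** The while-on-treatment label and the 7.2.5 window both point to a cut at end of treatment; on that reading nothing is biased. This stands as a competing reading. It contradicts the worded definition, however, and PFS and supplementary OS use the same label without that cut.
- **A reader might infer that follow-up scans are collected and then discarded.** They are not. PFS uses them, up to new therapy in one estimand and regardless of intercurrent events in the other.
- **A reader might infer bias against the more toxic arm.** Phase 2 does report poorer tolerability for the antibody than for control. But the 6% is an any-time rate for antibody monotherapy, and no rate is given for the combination or Arm B. Section 8.11 also lets Arm A participants stop the antibody and stay on trifluridine/tipiracil, so an antibody stop need not end all treatment. With equal true rates, the sign follows whichever arm has more stops without progression.
- **Consequence.** OR and DC are secondary and outside the OS testing sequence, and the randomised comparison was cancelled. This stands in full.

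**Conclusion.** The inconsistency is real and worth correcting, but limited. Read literally, the rule contradicts the stated estimand on discontinuation. Read narrowly, it agrees, but the text does not say so and leaves treatment switch open. It could lower ORR or DCR in the arm with more discontinuations without progression; which arm, and by how much, the documents cannot show.

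The 0.3 to 2.2 points of ORR (at d = 6%) and the shift of up to 4.9 points in the DCR difference are assumed illustrations. The latter needs every stop to precede the first qualifying scan, none in Arm B, and a DCR of 81.4% taken from anti-EGFR-naive patients. OS events, power and type I error are unaffected. With the randomised part cancelled, the practical remnant is the unnamed intercurrent events in the SAP 6.1 BOR rule.

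**What to change.** In protocol 10.1.2.4.2.4, replace the sentence with event-by-event handling:

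1. For OR, DC, DoR and TTR, exclude responses recorded after the start of further anti-cancer therapy. Include responses recorded after treatment discontinuation but before that therapy.
2. State the handling of treatment switch in both directions, and say whether stopping one agent only is a discontinuation, a switch or neither.
3. For DoR, also say whether progression or death after discontinuation counts.
4. Give TtPS2 and TTNT their own censoring rules. A rule about responses has no meaning for them, and the TTNT event is itself a listed intercurrent event.
5. Align the BOR window in 7.2.5 with this. In SAP 6.1, name the events meant and reconcile them with the follow-up e-CRF exclusion and the 30-day window.

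The cost is a few sentences. No new data are needed, and the sample size and OS testing plan do not change.
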